**TISCHMS-MSCNP-002
CLINICAL STUDY PROTOCOL**

NCT03355365

CLINICAL PROTOCOL: Summary Information

| | |
|--|--|
| TITLE | Autologous, Bone Marrow-Derived Mesenchymal Stem Cell-Derived Neural Progenitor Cells (MSC-NP), Expanded Ex Vivo; Administered Intrathecally |
| SPONSOR | Tisch MS Research Center of New York (Tisch MSRCNY) [name] [contact] |
| PROTOCOL NUMBER | TISCHMS-MSCNP-002 |
| VERSION NUMBER AND DATE | V8 08/26/2021 |
| PHASE OF CLINICAL INVESTIGATION | Phase II |
| IND NUMBER | 13889 |
| PRINCIPAL INVESTIGATOR | [name], FAAN Director and Chief Research Scientist Tisch MS Research Center of New York |
| NUMBER OF SITES | 1 |
| STUDY DESIGN | Phase 2, Double-Blind, Placebo-Controlled, randomized, Parallel Study of Intrathecal autologous MSC-NP Cells in Patients With MS |
| PRIMARY OBJECTIVE | To determine efficacy of multiple (6) intrathecal administrations of autologous MSC-NPs compared to placebo through assessment of disability outcomes |
| SECONDARY OBJECTIVES | To determine continued safety and tolerability of multiple intrathecal injections of MSC-NPs in patients with MS |
| NUMBER OF SUBJECTS | 50 |
| SUBJECT SELECTION CRITERIA | Inclusion Criteria (summary): SPMS or PPMS patients who have significant disability (EDSS between 3.0 and 6.5) that was not acquired within the last 12 months. Exclusion Criteria (summary): EDSS > 6.5, or anyone with comorbidities (past or present) that would put them at a higher risk for safety complications. |
| INVESTIGATIONAL NEW DRUG / INTENDED USE | Bone Marrow-Derived Mesenchymal Stem Cell-Neural Progenitor Cells (MSC-NP) for use as treatment for multiple sclerosis |
| CONTROL GROUP OR OTHER STUDY ARMS (if applicable) | Placebo (LP procedure) |
| DURATION OF SUBJECT | Subjects will participate in the study for 3 years |

| | |
|--|---|
| PARTICIPATION AND DURATION OF STUDY | 
 • Pretreatment screening and bone marrow aspiration: potentially up to 4 months • Treatment phase: 2 years, total 12 treatments (6 MSC-NP injections, 6 placebo lumbar punctures) every 2 months • Follow-up: 1 year |
| PRIMARY ENDPOINT | EDSS Plus (measured at baseline, month 6, month 13, month 20, month 27, and month 36) |

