9.3 Effectiveness analysis

All statistical analysis will be performed by [name] and her team. Descriptive statistics will be calculated for patients at baseline for the entire cohort

as well as by treatment status. Treatment and placebo group patients will be compared on continuous and discrete baseline characteristics to assess randomization. The EDSS-Plus scale [6] will be used as our primary endpoint with improvement on one or more of the 3 components (EDSS, T25FW and 9HPT). Improvement is defined as ≥ 1 point decrease from baseline EDSS if EDSS at entry is ≤ 5.5 , and a ≥ 0.5 point decrease from baseline EDSS if EDSS at entry is ≥ 6.0 , $\geq 20\%$ positive change in T25FW, and/or $\geq 20\%$ positive change in 9HPT confirmed. The primary endpoint of improvement on one or more of the 3 EDSS-Plus categories between treatment and placebo groups will be assessed bi-varately using the chi-square or Fisher's exact test, as appropriate, at year 1, 2, and 3 of the study. The three components of the EDSS-Plus composite score will also be assessed individually at all time points. A longitudinal linear mixed-effect model will be used to assess longitudinal change (percentage change in mean time) from baseline to 3 years for T25FW and 9HPT, with random intercepts for patients and taking into account treatment status (treatment vs placebo), progression status (SPMS vs PPMS) and time-progression status interaction. Secondary endpoints including 12-item walking scale and urodynamic studies (binary, $\geq 20\%$ improvement in bladder capacity vs $< 20\%$) will also be analyzed. Linear regression models for continuous outcomes and logistic regression models for discrete outcomes will be used to assess the independent effect of treatment status on secondary outcomes, controlling for co-variates. All analyses will be performed in SAS Version 9.4 (SAS Institute Inc., Cary, NC).

Any deviations from the previously described statistical plan will be described and justified in a protocol amendment and/or in the final report submitted to the IND application.

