### 1.2 Study Design

The study is a Phase II, double-blind, placebo-controlled, randomized, parallel group design with a compassionate crossover element. The IT-MSC-NP treatments and all clinical assessments take place at a single center (Tisch MSRCNY). Both the patient and the examining neurologist are blinded to the treatment. The treating clinician ([name], principal investigator) and the cell manufacturing coordinator ([name], co-PI) are not blinded. The total study duration is 3 years upon enrollment. Each subject will initially attend 1 screening visit, 1 visit for bone marrow extraction, and 1 baseline visit. In the first year, each subject will receive 6 intrathecal injections of MSC-NPs or placebo spaced 2 months apart, followed by an outcome assessment visit 3 months after the 6th treatment. In the second year, subjects will cross-over into the opposite group, and will receive 6 intrathecal injections of placebo or MSC-NPs spaced 2 months apart, followed by an outcome assessment visit 3 months after the 12th treatment. There is an additional follow-up visit at the end of year 3.

**Study Name:** Autologous, Bone Marrow-Derived Mesenchymal Stem Cell-Derived Neural Progenitor Cells, Expanded Ex Vivo; Administered Intrathecally (Phase II Trial)

**Principal Investigator:** [name]

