### **4 STATISTICAL ANALYSIS OF THE PRIMARY AND SECONDARY STUDY OBJECTIVES**

#### **4.1 Analysis of the Primary Study Objective**

##### Primary Outcome:

The primary analysis will include all subjects meeting inclusion and exclusion criteria and who have completed a year of treatment/placebo and the 3 month post-treatment assessment. EDSS Plus composite score from 3 month post-treatment assessment will be compared to baseline.

Descriptive statistics will be calculated for patients at baseline for the entire cohort as well as by treatment status. Treatment and placebo group patients will be compared on continuous and discrete baseline characteristics to assess randomization.

The EDSS-Plus scale will be used as our primary endpoint with improvement on one or more of the 3 components (EDSS, T25FW and 9HPT). Improvement is defined as  $\geq 1$  point decrease from baseline EDSS if EDSS at entry is  $\leq 5.5$ , and a  $\geq 0.5$  point decrease from baseline EDSS if EDSS at entry is  $\geq 6.0$ ,  $\geq 20\%$  positive change in T25FW, and/or  $\geq 20\%$  positive change in 9HPT confirmed. The primary endpoint of improvement on one or more of the 3 EDSS-Plus categories between treatment and placebo groups will be assessed bi-varately using the chi-square or Fisher's exact test, as appropriate, at year 1, 2, and 3 of the study. Adjusted odds ratio (95%CI) between treatment and placebo groups at each time point will be estimated through mixed effect logistic regression with fixed effect of time, treatment, relevant covariates, and random effect of patients. The three components of the EDSS-Plus composite score will also be assessed individually at all time points. A longitudinal linear mixed-effect model will be used to assess longitudinal change (percentage change in mean time) from baseline to 3 years for T25FW and 9HPT, with random intercepts for patients and taking into account treatment status (treatment vs placebo), disease subtype (SPMS vs PPMS) and time-progression status interaction.

**Study Name:** Autologous, Bone Marrow-Derived Mesenchymal Stem Cell-Derived Neural Progenitor Cells, Expanded Ex Vivo; Administered Intrathecally (Phase II Trial)

**Principal Investigator:** [name]

Under parallel design, we will compare the outcomes of interest between the two study treatments, with outcomes at 1 year as the primary time point, secondary analyses will evaluate outcomes at years 2 and 3.

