### Exploratory Outcomes:

Individual MRI measures obtained from NeuroQuant software will be analyzed as an exploratory outcome. Brain, cervical and thoracic spine MRI scans will be obtained at baseline, and at months 13, 27, and 36. Assessments will include the following:

- Proton density and T2-weighted two-dimensional (2D) multislice turbo/fast spin-echo
- T1-weighted three-dimensional (3D) spoiled gradient recalled echo both pre-contrast and after a 10 minute delay following injection of gadolinium post-contrast sequencing
- 2D T2 weighted Fluid -Attenuated Inversion Recovery (FLAIR)
- MTR MR tractography dependent on the number of tracts followed
- DTI – A T2 SPC 3D Flair sagittal sequence, EP diffusion, and a gradient filed mapping

Using the CorTechs NeuroQuant software package a multi-structure atrophy report will be generated for all brain MRI scans as well as a Lesion Quant Flair assessment of total number and volume of lesions; the total number and volume of enlarging lesions and the total number and volume of new lesions. All lesions to be counted would have to be at least 3 voxels in size. For lesions to be considered enhancing an increase in intensity by at least 20% on the post-contrast images compared to the baseline T1 sequence lesions. The total number of new or enlarging T2 hyperintense lesions as detected by MRI will be assessed by a negative binomial model. Percentage change in total brain volume from baseline to month 13 will be assessed using an MMRM analysis.

CSF biomarker analysis will also be included as an exploratory outcome. CSF, plasma, and serum samples will be obtained at the time of each treatment, and 3 months following the 12th treatment, for a total of 13 samples of each type.

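### Random intercepts alone in the 36-month T25FW and 9HPT models give wrong standard errors, in both directions, if patients change at different rates

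*SAP*

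**What the plan says.** SAP 4.1 (Primary Outcome) sets up a linear mixed model to "assess longitudinal change (percentage change in mean time) from baseline to 3 years for T25FW and 9HPT". The SAP then specifies its terms: the model is to be fitted "with random intercepts for patients and taking into account treatment status (treatment vs placebo), disease subtype (SPMS vs PPMS) and time-progression status interaction". Protocol 9.3 has the same model: "with random intercepts for patients and taking into account treatment status (treatment vs placebo), progression status (SPMS vs PPMS) and time-progression status interaction". In both, the patient intercept is the only random term. Neither document gives a random slope, a residual covariance structure, robust standard errors or a degrees-of-freedom method. Neither says whether time is linear or a visit factor, and neither lists a treatment-by-time term.

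The protocol synopsis gives the visits: "EDSS Plus (measured at baseline, month 6, month 13, month 20, month 27, and month 36". SAP 1.2 adds that "In the second year, subjects will cross-over into the opposite group". The documents do not define treatment status after that switch, although SAP 4.1 leans towards the randomised arm: "Under parallel design, we will compare the outcomes of interest between the two study treatments, with outcomes at 1 year as the primary time point".

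Two other analyses matter here. For brain volume the SAP already uses a more flexible model: "Percentage change in total brain volume from baseline to month 13 will be assessed using an MMRM analysis". The primary endpoint does not use the linear model at all; it "will be assessed bi-varately using the chi-square or Fisher's exact test, as appropriate, at year 1, 2, and 3 of the study".

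**The concern.** A random intercept alone implies one variance at every visit and one correlation for every pair of visits. If patients with progressive MS change at different speeds over 36 months, variance grows with time and nearby visits correlate more than distant ones. The fitted model averages this out.

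A contrast that runs along time then gets a standard error that is too small. A contrast at a late visit is also too liberal, and one at an early visit is too conservative. At stake are the p-values and intervals for continuous change in two of the three EDSS-Plus components: chance differences in slope could pass as effects, and precision would be lost at Month 13, which the plan makes its main time point.

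**Working it through.** **The plan's own figure.** The documents give no SD, power or error rate for these models. The stated power (more than 80% with 20 per group, 40% versus 5%) belongs to the binary endpoint. Exact enumeration of the pooled Z-test gives 82.0%, so it reproduces, but it has no bearing here.

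**Inputs.**
- Post-baseline visits at Months 6, 13, 20, 27 and 36 (synopsis), T = 5.
- Two-sided 5% level.
- Assumption, not in the documents: s, the between-patient SD of slope per year in units of the residual SD at a visit, from 0 to 1.5. Over three years, s = 0.25, 0.5, 1.0 and 1.5 means an SD of true 36-month change of 3s = 0.75, 1.5, 3.0 and 4.5 residual SDs.
- Assumption: intercept variance equals residual variance (both 1), independent of slope. For change from baseline this is roughly what noise in the baseline measurement produces.

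**Step 1: time-by-subtype, time linear, 1 df.** Mean visit time is 20.4 months and Sxx = 549.2 months² = 549.2/144 = 3.814 years². With q = s² × Sxx, true variance divided by model variance is (1 + q)/(1 + q/4). The type I error is 2[1 − Φ(1.96/√ratio)].

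| s | q | ratio | type I error |
|---|---|---|---|
| 0 | 0 | 1.00 | 5.0% |
| 0.25 | 0.238 | 1.17 | 7.0% |
| 0.5 | 0.954 | 1.58 | 11.9% |
| 1.0 | 3.814 | 2.46 | 21.2% |
| 1.5 | 8.581 | 3.05 | 26.1% |

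Simulation of the REML fit with 40 patients gives 5.6%, 12.2%, 21.8% and 26.4% at s = 0, 0.5, 1.0 and 1.5; with 50 patients it gives 21.2% at s = 1.0. Keeping baseline as a sixth visit raises the closed-form value at s = 1.0 to 27.5%.

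If time is a visit factor and the interaction is a joint 4-df test, the excess is diluted. The statistic is then [(1 + q)χ²₁ + χ²₃]/(1 + q/4), compared with 9.49. It exceeds that 5.1%, 5.6%, 7.8% and 9.6% of the time at s = 0.25, 0.5, 1.0 and 1.5.

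**Step 2: treatment terms, by simulation (20 per arm; s = 0.5, 1.0, 1.5).**
- Randomised arm, main effect only: 4.9%, 5.0%, 5.1%.
- Arm-by-time, if added: 12.6%, 22.0%, 26.9%.
- Current treatment, Month 36 coded as the last procedure received: 10.1%, 16.7%, 21.1%.
- Current treatment, Month 36 coded as off treatment: 6.8%, 6.9%, 7.5%.

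**Step 3: arm contrasts at one visit, if taken from this model.** The model uses the average variance over visits, 2 + s² × mean(t²), where mean(t²) = (0.25 + 1.174 + 2.778 + 5.063 + 9)/5 = 3.653. The true variance is 2 + 1.174s² at Month 13 and 2 + 9s² at Month 36. The ratio k of model SE to true SE is the square root of the quotient, and the type I error is 2[1 − Φ(1.96k)].

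| s | model | Month 13 true | k | type I | Month 36 true | k | type I |
|---|---|---|---|---|---|---|---|
| 0.5 | 2.913 | 2.293 | 1.13 | 2.7% | 4.25 | 0.83 | 10.5% |
| 1.0 | 5.653 | 3.174 | 1.33 | 0.9% | 11.00 | 0.72 | 16.0% |
| 1.5 | 10.219 | 4.641 | 1.48 | 0.4% | 22.25 | 0.68 | 18.4% |

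Simulation agrees: 2.9%, 0.8% and 0.4% at Month 13, with standard errors about 14-49% too large, and about 11-19% at Month 36.

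**The case against.** The only treatment term listed is a main effect, and the SAP describes a parallel comparison. Read as the randomised arm, that test holds its level: 4.6-5.8% over all settings tried with 40 or 50 patients, including 20% dropout. The one inflated test that both documents name, time-by-subtype, serves no stated objective or endpoint and rests on 10 PPMS patients. The primary test and the T25FW and 9HPT secondary endpoints (20% improvement, yes or no) do not use this model. Eligibility also requires stable disease, which may limit variation in slope. All of this stands, and it limits how much the point matters.

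A reader might still infer that every test from these models is anti-conservative, or that a treatment effect could be claimed at two to five times the nominal rate. The documents do not support that. Inflated treatment tests need either an arm-by-time term that is not listed or a crossover coding that is not settled. The direction reverses at Month 13. The two-to-five multiple needs a slope SD of about 0.5 or more and linear time, neither of which is stated. Nor does the 40% response assumption show that slopes vary: a common shift plus visit noise can produce it.

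The safe reading has its own cost. A randomised-arm main effect averages Months 6 to 36 across a crossover in which every patient receives both treatments, so it keeps 5% but does not compare change over time, which is the model's stated purpose.

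**Conclusion.** The point holds for terms that vary over time, in a supplementary continuous analysis. If slopes differ between patients, time-by-subtype as a linear-time test is too liberal (about 7-26% for slope SDs of 0.25-1.5), and less so as a joint visit-factor test. Arm contrasts by visit would be too liberal at Month 36 and too conservative at Month 13. The size rests on an assumed slope SD and, for the visit contrasts, on the assumed intercept variance. With no slope variation all these tests hold about 5%. The change is worth making because it is cheap and gives the Month 13 contrast a correct standard error; it does not put the primary result in doubt.

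**What to change.** In SAP 4.1 and Protocol 9.3, replace the random-intercept specification for T25FW and 9HPT with an MMRM: randomised arm, visit as a factor, arm-by-visit, subtype, subtype-by-visit, unstructured within-patient covariance and Kenward-Roger degrees of freedom. Name the fallbacks in order if it does not converge: random intercept plus random slope, then heterogeneous Toeplitz. State that treatment status means the randomised arm, and take the Month 13 arm contrast as the main estimate from this model.

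The cost is a paragraph of text and a different covariance statement in software the plan already names. Five visits need 5 × 6/2 = 15 covariance parameters, so non-convergence is possible with about 40-50 patients. If slopes vary, intervals will be wider for late-visit and slope contrasts and narrower at Month 13.

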## 1.5 Sample Size and Randomization

A total of 50 study subjects will be enrolled based on power analysis based on 20 participants in each group of the Phase II study. Group sample size of 20 in the treatment group and 20 in the placebo group achieve more than 80% power to detect a difference between the group proportions of 35%, using a two-sided Z-test with pooled variance and using a significance level of 0.05. This calculation assumes that 40% of patients in the treatment group and 5% of patients in the placebo group achieve at least one of the EDSS-Plus components. The prevalence of patients with improved outcome is informed by the results of our Phase I trial, in which 40% of patients experienced a decrease of 0.5 or more on EDSS. A total of 50 patients (25 patients in each group) will initially be enrolled to account for an expected attrition rate of 20%.

Subjects will be stratified according to baseline EDSS score (3.0-4.0, 4.5-5.5, 6.0, and 6.5) and disease subtype (SPMS or PPMS), and block randomized within each stratum. The total number of subjects to be enrolled in each subgroup is shown below. Subjects are stratified and block randomized into placebo or treatment group in order of date of enrollment based on randomization scheme designated by [name]. Study subjects are randomized in an equal fashion to study treatment and placebo at initial randomization.

EDSS	SPMS	PPMS
3.0-4.0	10	4
4.5-5.5	10	2
6.0	10	2
6.5	10	2
Total # of patients:	40	10

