For comparisons via association tests, number (%) of events in the two groups and p-values from Chi-squared or Fisher's exact test will be reported. For regressions, odds ratios (95% CI) between the two groups and p-values from the mixed-effect model will be reported.

Appropriate method to deal with missing values will be chosen after exploring the data collected. Based on reason(s) and amount of missingness, deletion and/or imputation might be applied.

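### The only interval estimate planned for the primary endpoint is a patient-specific odds ratio, which will not match the group percentages reported beside it

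*SAP*

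**What the plan says.** SAP 4.1 tests the primary endpoint (improvement on at least one EDSS-Plus component, with one year as the primary time point) by chi-square or Fisher's exact test. From that comparison it reports counts, percentages and a p-value.

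The effect size comes from a second analysis: "Adjusted odds ratio (95%CI) between treatment and placebo groups at each time point will be estimated through mixed effect logistic regression". The fixed effects are time, treatment and covariates, and the random effect is the patient. The reporting rule is "For regressions, odds ratios (95% CI) between the two groups and p-values from the mixed-effect model will be reported".

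The sample size in SAP 1.5 (and protocol 9.2) is set on a difference in proportions. It "assumes that 40% of patients in the treatment group and 5% of patients in the placebo group" will improve on at least one component.

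Neither document says whether the odds ratio is meant to be conditional or marginal. Neither plans a risk difference, a standardised estimate or a GEE (generalised estimating equations) analysis. Neither gives a random-effect variance or intraclass correlation.

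**The concern.** In a logistic model with a random patient intercept, the exponentiated treatment coefficient compares the odds of improvement at the same value of the patient effect. Averaging over patients to get the proportion improved in each arm pulls the odds ratio towards 1, because the logistic curve is not linear. The model's odds ratio and the one implied by the two percentages are therefore different quantities whenever patients vary and treatment has an effect.

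The SAP places the two side by side and describes the first as a contrast between the groups. A reader who takes it as the group effect would overstate the benefit. No other interval is planned for this endpoint, so a reader who wants the size and uncertainty of the group effect has no prespecified figure to use. Adding a treatment-by-time term, or dealing with empty cells, would not remove the mismatch.

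**Working it through.** **Inputs.** From SAP 1.5: improvement 40% v 5%; "Group sample size of 20 in the treatment group and 20 in the placebo group"; "using a two-sided Z-test with pooled variance and using a significance level of 0.05". From SAP 4.1: a random-intercept logistic model. Not given anywhere: the random-intercept SD, σ. It is varied below through the latent intraclass correlation, ICC = σ²/(σ² + π²/3).

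**The plan's own figure.** Exact enumeration of the two-sided pooled Z-test at 20 v 20 gives power of 82.0%, which agrees with the stated figure of more than 80%. The normal approximation gives 77.7%. Enrolment is 40/(1 − 0.20) = 50. The rates are therefore usable as the plan states them.

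**Group odds ratio.** (0.40/0.60)/(0.05/0.95) = 12.67.

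**Conditional odds ratio.** For each σ, find the arm logits η₁ and η₀ for which the mean of expit(η + σZ), Z standard normal, equals 0.40 and 0.05 (Gauss-Hermite quadrature, 150 nodes). The conditional odds ratio is exp(η₁ − η₀). For example, at ICC 0.5, σ = 1.81, η₁ = −0.631 and η₀ = −4.198, so the odds ratio is exp(3.567) = 35.4.

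| Assumed ICC | σ | Conditional OR, 40% v 5% | Ratio to 12.67 | Ratio to group OR, 40% v 20% (group OR 2.67) |
|---|---|---|---|---|
| 0.1 | 0.60 | 14.4 | 1.1 | 1.1 |
| 0.3 | 1.19 | 20.4 | 1.6 | 1.3 |
| 0.5 | 1.81 | 35.4 | 2.8 | 1.6 |
| 0.7 | 2.77 | 100 | 7.9 | 2.6 |

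At 40% v 30% the ratio is about 1.3 at ICC 0.5 and 1.6 at ICC 0.7.

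**Which ICC is plausible?** Every visit is scored against one baseline. For a single continuous measure with equal, independent variation at each visit, two changes from that baseline correlate at 0.5. The endpoint, however, is improvement on any of three measures, with 9HPT counted in either hand. Take k = 3 or 4 independent components, each with change scores correlated 0.5 between two visits. Set each component's rate to 1 − (1 − p)^(1/k), so that the composite rate is p, then find the random-intercept model with the same probability of improvement at both visits. The ICC is 0.34 (p = 40%) and 0.42 (p = 5%) for k = 3, and 0.31 and 0.39 for k = 4. At 40% v 5%, ICC 0.31 to 0.42 corresponds to a ratio of about 1.6 to 2.2. Positively correlated components or a lasting response would raise it. These are modelling assumptions, not trial data.

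**Empty cells.** At a 5% placebo rate and 20 per arm, the chance of no placebo responder at Month 13 is 0.95²⁰ = 0.36. In that event an ordinary Month 13 odds ratio has no finite estimate, which limits the choice of remedy.

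**The case against.** The strongest reply is that this is a choice of estimand, not an error. A conditional odds ratio is a legitimate target, the SAP already calls it adjusted, and a contrast between groups is ordinary language for any treatment effect. The endpoint is tested by chi-square or Fisher, and the reported counts give the risk difference and crude odds ratio by simple arithmetic. Most of this stands, and it limits the point to labelling and a missing estimate.

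Two parts of the reply do not hold. The word adjusted tells a reader that covariates were controlled. It does not say that the figure also conditions on an unobserved patient effect, and the mismatch would exist with no covariates at all. Leaving readers to derive the group effect also leaves its interval unspecified, although at these counts the choice of method matters.

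Some stronger readings are tempting but unsupported:

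- **That the odds ratio will be 2 to 8 times too large.** At 40% v 5% this needs an ICC of about 0.39 to 0.70. Neither document gives one, and the factor shrinks as the placebo rate rises.
- **That the model gives a within-patient odds ratio.** Up to Month 13 the arms are parallel, so treatment varies only between patients. The right term is patient-specific, or conditional.
- **That the interval is for the wrong quantity.** This presumes a marginal target that the SAP never states.
- **That inflation can be projected over all five post-baseline visits at 40% v 5%.** Months 20, 27 and 36 follow the crossover, so a sustained contrast between the arms is not what the plan assumes.

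**Conclusion.** The point holds as a gap in labelling and estimation. The primary endpoint's only planned interval belongs to a patient-specific odds ratio. With a real effect and any patient variation, that figure lies further from 1 than the odds ratio implied by the adjacent percentages.

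The direction is certain; the size is not. At the planning rates the inflation runs from 1.1 times (ICC 0.1) to 7.9 times (ICC 0.7). The shared baseline makes an ICC of about 0.3 to 0.4 or more plausible, which is roughly 1.6 to 2 times or more. At 40% v 20% it is about 1.1 to 2.6 times across the whole ICC range. All of these figures rest on a normally distributed random intercept and an assumed ICC.

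A reader might infer that the primary significance test is compromised. It is not: the chi-square or Fisher test and the percentages do not use this model. The two odds ratios also coincide at 1 when there is no effect.

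**What to change.** In SAP 4.1:

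1. Name the Month 13 risk difference as the group-level effect measure for the primary endpoint, with a 95% interval by one prespecified method that tolerates small or empty cells. Options are a Newcombe interval, an exact unconditional interval, or a standardised estimate from penalised logistic regression. This puts the estimate on the same scale as the 35-point difference behind the sample size.
2. If a marginal odds ratio is also wanted, obtain it by a penalised or exact method, given the 36% chance of no placebo responder at the planning rate.
3. Keep the mixed-model odds ratio as supportive. Label it patient-specific (conditional on the random effect), and note that it is not expected to agree with the percentages.

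The cost is SAP wording and slightly more analysis work. No new data are needed and the primary test does not change. The sponsor would be presenting a less striking effect size.

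### The Month 13 odds ratio promised in SAP 4.1 has no finite maximum-likelihood estimate if no placebo subject improves, a 28–36% chance under the plan's own 5% placebo rate, and no fallback is given

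*SAP*

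**What the plan says.** SAP 4.1 (Primary Outcome) compares the proportion improved on EDSS-Plus between groups by a chi-square or Fisher's exact test, with one year (Month 13) as the primary time point. It then plans an adjusted odds ratio with a 95% interval at each time point, from "mixed effect logistic regression with fixed effect of time, treatment, relevant covariates, and random effect of patients".

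For the association tests it will report counts, percentages and p-values. For the regressions, "odds ratios (95% CI) between the two groups and p-values from the mixed-effect model will be reported". No other between-group estimate with an interval is planned for the composite.

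The listed fixed effects contain no treatment-by-time interaction. The covariates are not named. Nothing says whether treatment means randomised group or current treatment once subjects have crossed over in year 2 (SAP 1.2). Neither document says what is reported if a cell is empty or the model fails to converge.

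SAP 1.5, like protocol 9.2, sets the expected rates: "This calculation assumes that 40% of patients in the treatment group and 5% of patients in the placebo group achieve at least one" of the components. It plans 20 evaluable and 25 enrolled subjects per arm.

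**The concern.** A 5% rate in an arm of 20 to 25 means about one expected improver, so an empty placebo cell at Month 13 is an ordinary outcome. When it occurs, the likelihood for a Month-13-specific odds ratio keeps rising as the odds ratio grows. The software then stops at an arbitrary large coefficient with a huge standard error.

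The trial could therefore have a clearly significant primary test and no usable effect estimate or interval to go with it. The analyst would have to choose a rescue method after seeing the data, and the reasonable choices give very different intervals. The alternative is the main-effects model exactly as listed, which can return a finite number that is not the Month 13 odds ratio.

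**Working it through.** **Inputs.** Improvement rates of 40% (treatment) and 5% (placebo), 20 evaluable and 25 enrolled per arm, two-sided pooled Z-test at 0.05, 20% attrition: SAP 1.5. Analysis set of subjects completing year 1 and the 3-month post-treatment assessment: SAP 4.1. Visits at Months 6, 13, 20, 27 and 36: SAP 1.3.1.

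**The plan's own figures.** SAP 1.5 states: "Group sample size of 20 in the treatment group and 20 in the placebo group achieve more than 80% power".
- Normal approximation: mean rate 0.225; null SE = √(2 × 0.225 × 0.775/20) = 0.1320; alternative SE = √((0.40 × 0.60 + 0.05 × 0.95)/20) = 0.1199. Power = Φ((0.35 − 1.96 × 0.1320)/0.1199) = 77.7%.
- Exact enumeration of the same test gives 82.0%, so the stated power reproduces.
- Enrolment: 40/(1 − 0.20) = 50, which also reproduces.

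**Chance of an empty placebo cell at Month 13.** P = (1 − 0.05)^n.
- n = 20: 0.95^20 = 35.8%
- n = 25: 0.95^25 = 27.7%

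**How often the primary test is significant in that case.** With no placebo improver, Fisher's p falls to 0.05 or below from 5/20 treated improvers (p = 0.047) or 6/25 (p = 0.022). At a 40% treatment rate this has probability 95% (n = 20) or 97% (n = 25). So 0.358 × 0.95 = 34% of trials at n = 20, and 0.277 × 0.97 = 27% at n = 25, would have a significant primary test and no finite Month 13 odds ratio by ordinary maximum likelihood.

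**Illustration: 8/20 treated, 0/20 placebo (single-visit data).**

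| Method | Result |
|---|---|
| Fisher's exact test | p = 0.0033 |
| Ordinary logistic fit | coefficient 23.2, SE about 17,800, Wald p = 0.999; these values mark only where iteration stopped |
| Exact conditional odds ratio | 95% CI 2.26 to infinity |
| Odds ratio with 0.5 added to each cell | 27.9 (1.5 to 526) |
| Risk difference, score interval | 0.40 (0.22 to 0.62) |

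**The longitudinal model.** Random-intercept logistic models were fitted by maximum likelihood to eight simulated datasets with no placebo improver at Month 13. The rates at other visits and the random-intercept SDs (1 and 2) are assumptions, used only to show whether an estimate exists.
- With treatment-by-time, which an odds ratio at each time point requires, the Month 13 log odds ratio ran to about 16 to 23 every time. It has no finite estimate.
- With only the listed main effects over all five visits, the log odds ratios were finite, about 0.06 to 1.9. The single treatment coefficient draws on later visits, after placebo-first subjects have received cells.
- If the main-effects model used only Months 6 and 13, separation would need no placebo improver at either visit. Assuming 5% at each, that has a chance of about 13–17% (n = 20) or 8–10% (n = 25).

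**The case against.** The strongest reply is that the SAP's model, read literally, does not fail. It has no treatment-by-time term, so an empty Month 13 placebo cell alone does not separate it. This is correct. A reader might infer that every planned odds ratio becomes inestimable whenever no placebo subject improves at Month 13, and the documents do not support that. But the literal model yields one treatment coefficient across visits on both sides of the crossover, not the odds ratio at each time point that the same sentence promises. Either the model is extended and can fail, or it stays finite and answers another question.

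A reader might also infer that the primary result is at risk. It is not: the chi-square or Fisher p-value and the counts are unaffected, and a risk difference can be computed from the counts. What is missing is a planned interval for it.

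Nor does the SAP name maximum likelihood or Wald limits. Under separation, a likelihood-ratio p-value and a one-sided profile limit remain informative, so a Wald p near 1 is not the inevitable output. The point concerns ordinary fitting with no stated alternative.

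A further tempting inference, that the random effect itself makes separation more likely, has no support in the documents or the calculations.

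Finally, 28–36% depends on the 5% rate. At an assumed 10% it is 0.90^25 to 0.90^20 = 7% to 12%, and at 15% it is 2% to 4%. The 5% is, however, the rate on which the trial was sized.

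**Conclusion.** The point holds in a limited form. Under the plan's own 5% placebo rate and 20 to 25 evaluable placebo subjects, there is a 28–36% chance that a Month-13-specific odds ratio has no finite maximum-likelihood estimate or Wald interval. The SAP supplies no substitute. The main-effects model as listed may avoid this only by pooling across the crossover, so the text needs correcting either way.

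The percentage belongs to Month 13 alone. The 5% assumption does not describe the placebo-first group after it receives cells, so the figure should not be carried to Months 20 to 36. The three components, analysed separately, are at least as exposed at Month 13, since none can have more placebo improvers than the composite.

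The correction should be made, but it does not threaten the primary test.

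**What to change.** Amend SAP 4.1 before the Month 13 data are unblinded for analysis:

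1. Report the Month 13 risk difference between randomised groups with a Miettinen–Nurminen (score) or Newcombe 95% interval, beside the chi-square or Fisher p-value.
2. If an adjusted Month 13 odds ratio is kept, estimate it from Month 13 data by Firth-penalised logistic regression with profile-likelihood limits, or by exact conditional logistic regression. Name the covariates.
3. In the longitudinal model, include treatment-by-time, define treatment as randomised sequence, and label the model supportive.

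The cost is SAP wording and a small amount of extra analysis, with methods available in the SAS and R versions that the SAP already names. The downside is that the Month 13 estimate does not borrow information from other visits.
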